4.4 Endpoints

Primary Endpoint:

The difference between AirRR and ManCRR, which is greater than -3 establishes non-inferiority. The unit in this calculation is bpm and sampling rate is 1 Hz.

Secondary Endpoints:

1. The accuracy of inhalation classification in the segmentation basis is greater than 82.5% at the 95% Cl. The performance metrics (F1-socre, MAPE) at event level will be demonstrated and target for F1-score > 0.8, MAPE < 0.5.

2. To measure the agreement of AirRR and ManCRR on concordance correlation coefficient, and on their mean and bias by Bland-Altman analysis.

3. Use paired t-test to compare the response time of Airmod versus Capnography on Capnostream[™]35 after administration of jaw thrust. In the target of p<0.05 indicates significance.

4.1. The difference of ManCRR minus AirRR and ManCRR minus CapRR indicates non-inferiority at margin of 3 bpm (M1) and sampling rate 1Hz.

4.2. The difference of ManCRR minus AirRR and ManCRR minus CapRR indicates non-inferiority at margin of 2 bpm (M2) and sampling rate 1Hz.

5. The absence of unanticipated serious adverse device effect (USADE) during study period and the questionnaire.

Evaluating the Non-Inferiority of Airmod to Capnostream™35 on Respiratory Rate Monitoring and User Experience Clinical Evaluation

[Time Frame:

Non-Anesthesia Stage: Up to 40 patients will be randomly assigned to non-anesthesia stage assessment, the measurement will be evaluated after enrollment with ICF, at the non-operating room (NOR) area. (5~30 minutes)

Procedure Stage: From firstly anesthetic administration to end of procedure. (Depends on procedure 10mins ~ few hours)

Transportation Stage: During transportation of subjects. (1~10 minutes)

Post anesthesia care unit stage : From subjects arrive post anesthesia care unit (PACU) to discharge from PACU (PAR or PADSS score \geq 9) (At least 15 minutes)]

5 Study Methods

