7.2 Analysis Populations

(ICH E3; 9.7.1, 11.4.2.5. ICH E9; 5.2)

In our study design, both experimental and reference devices are set on all patients enrolled. The analysis is comparing the recording of devices on identical subjects. Therefore, all of the intending to treat patients are included in our study. However, if the patients were at risk of life-threatening events during their operation, the medical crew is obligated to proceed with resuscitation and stop the intervention, in such case, the recording could be terminated and the previous data is still counted in our study.

| Population | Definition / Criteria | Analyses Evaluated |
|-----------------|--|---|
| Safety | All subjects who are enrolled in the study. This population will be based on the operation the subject actually received. | Safety Adverse events/Adverse devices related events. |
| Intent To Treat | Comprise of all subjects with at least 5 minutes recording to evaluate the efficacy. This population will be based on the recording of both devices to the subjects enrolled. | Efficacy |
| Per-Protocol | The per-protocol population is a subset of the ITT population in this study. Subjects who were enrolled in the study and recorded by both devices for more than 5 minutes will be part of the ITT groups and the subjects with a protocol violation that is deemed to affect efficacy assessments in the study period, but their data will be | Per Protocol Population. |

Evaluating the Non-Inferiority of Airmod to Capnostream[™]35 on Respiratory Rate Monitoring and User Experience Clinical Evaluation

| excluded from the period(s) affected by the protocol violation for a PP analysis. (For instance, a patient who was administrated with an advanced airway management tool (LMA) should be considered as a protocol violation in the intraoperative period.) | | |
|---|--|--|
|---|--|--|

Table 3. Analysis populations

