7.5.5 Adjustment of p-value

On the confidence interval analysis in this study, we adopt OBrien-Fleming to determine the nominal significance level α =0.00153 at the interim analysis for the 150 samples. Furthermore, at the end of the study the O'Brien-Fleming determines the nominal significance level at 0.02450 to establish the target of our study confidence interval.

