8.2.5 Bland-Altman analysis

The Bland-Altman analysis is widely used to measure the consistency of continuous data from two distinct measurements. It combines the quantitative analysis of LoA (limits of agreement) and the qualitative analysis of scatter plot to show an instinctive evaluation between two methods of their correlation. Each of the n samples is then represented on the graph by assigning the mean of the two measurements as the x-value, and the difference between the two values as the y-value. The repeatability of RR measurements from Airmod (AirRR) and CapnostreamTM35(K150272, Medtronic) (CapRR) will be compared with ManCRR separately under the sampling rate: 1 sample point per 60 seconds, the differences are representing into Δ G_A and Δ G_E, while the S(x,y)=((Δ G_A+ Δ G_E)/2, Δ G_A- Δ G_E). To compare an estimate of this to the LoA, the two LoA are the mean value of x separately ±1.96SD. (doi: 10.1080/10543400701329422)

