The primary efficacy analysis of primary endpoints are comparing the difference of AirRR and ManCRR to reject the null hypothesis (difference of estimation is greater than the non-inferiority limit : -3) under 95% level of confidence interval of all ITT population. The $\mu\alpha$ denotes the respiratory counts of AirRR per minute, and the $\mu\beta$ denotes the respiratory counts of ManCRR per minute. The respiratory count per minute is the mean of recorded samples (eliminating the missing or non-detecting data

point) in each minute. Respiratory counts per minute represent the respiratory rate and are tested in the primary objective hypothesis with the type I error of 0.025, and Type 2 error of 0.2, and the power is 0.8 with single tail non-inferiority analysis.

| Step | Summary |
|-------------------------------|---|
| Objective | Non-inferiority: H0:μα-μβ> d _{NI} vs H1:μα-μβ≤ d _{NI} |
| Endpoint | Margin_1 >-3; Margin_2 >-2 |
| Error | Type I error α=0.025 (one-sided) |
| | Type II errorβ=0.2, Power 1-β=0.8 |
| Non-inferiority limit | d _N = -3 Brpm |
| Population standard deviation | σ=3.29647 |
| Others | r=1, dropout rate=0.3% |

Reference from our pilot study in 25 cases

Table 6. Statistical information referencing from pilot study

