9.1.1 Secondary Analyses of Primary Efficacy Endpoint

The primary efficacy analysis will be further divided into three periods of study 1.Induction (3minutes from DIN), 2.Intraoperative period, 3.PACU period to reveal the performance of our device in particular scenarios. The data will be analyzed on a minute basis, and also aggregated per subject basis in each period. The candidates in the non-anesthesia group will be solely analysis for the whole period to represent the normal patient group in a healthcare facility.

| Look | Info Fraction | Approx. Cum. Subjects | Nominal Significance Level (1-sided) | Efficacy Boundaries z-scale |
|---------|---------------|-----------------------------|--|-----------------------------------|
| Interim | 50% | 150 | 0.00153 | 2.9626 |
| Final | 100% | 300 | 0.02450 | 1.9686 |

Fig 6. Information of Interim analysis

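### The visible text of SAP 9.1 tests per-minute counts without naming the unit of inference for the overall primary test, while the interim boundaries count subjects

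*SAP*

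**What the plan says.** - **Variable tested.** SAP 9.1: "The respiratory count per minute is the mean of recorded samples" within each minute, leaving out missing and non-detected points. It continues: "Respiratory counts per minute represent the respiratory rate and are tested in the primary objective hypothesis".
- **Period analyses.** SAP 9.1.1: "The data will be analyzed on a minute basis, and also aggregated per subject basis in each period". It does not say which of the two decides, and it does not cover the overall primary test.
- **Interim design.** The table in 9.1.1 counts information under "Approx. Cum. Subjects": 150 (50%, one-sided 0.00153, z 2.9626) and 300 (100%, 0.02450, z 1.9686). SAP 7.5.5 sets the interim level "at the interim analysis for the 150 samples".
- **Recording length.** The ITT population in SAP 7.2: "Comprise of all subjects with at least 5 minutes recording to evaluate the efficacy". The procedure stage in SAP 4.4: "Depends on procedure 10mins ~ few hours". The PACU stage adds at least 15 minutes.
- **Other units in use.** The endpoint is sampled at 1 Hz, MAPE (8.2.4) divides by recording minutes, and Bland-Altman (8.2.5) works "under the sampling rate: 1 sample point per 60 seconds".
- **Protocol.** Section 9.4.2 calls the test paired, with intervals of 99.69% (interim) and 95.1% (final). It does not say what the pair is and refers to the SAP.
- **SD.** SAP Table 6 gives 3.29647 from a 25-case pilot and does not say whether it is per minute or per subject.

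**The concern.** Minutes from one patient share that patient's anatomy, sensor placement and sedation course, so their AirRR minus ManCRR differences are likely to be correlated. An interval that counts each minute as a separate observation overstates the information, and the excess grows with recording length. Pooling minutes also lets long procedures dominate the estimate, so it changes what is estimated as well as its precision. The group-sequential boundaries assume that 150 of 300 subjects is half the information, and that need not hold if information is counted in minutes. The study is not blinded, and SAP 7.5.6 gives the interim information to the sponsor and investigators. A unit left open could therefore be chosen after results are known.

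**Working it through.** **1. The plan's own boundaries.** Lan-DeMets spending of O'Brien-Fleming type, one-sided 0.025, at information fraction 0.5: 2[1 − Φ(2.2414/√0.5)] = 0.001525, z = 2.9626. Solving the final boundary with correlation √0.5 gives z = 1.9686, one-sided 0.02450. Both match the SAP, and the implied intervals are 1 − 2(0.00153) = 99.69% and 1 − 2(0.0245) = 95.1%. The boundaries are sound if subjects carry the information.

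**2. Assumptions for the illustration.** The documents give neither minutes per patient nor within-patient correlation. I assume m = 30 minutes for every patient, ICC 0.1 to 0.5, and 3.29647 as the per-minute SD of the AirRR − ManCRR difference. For the BMI ≥ 30 subgroup I take the planned minimum of 30 patients and the final z.

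**3. Interval width.** Naive half-width = z × 3.29647/√(30n). Correct half-width = naive × √DEFF, with DEFF = 1 + 29 × ICC, which is 3.9 at ICC 0.1 (√ = 1.975) and 15.5 at ICC 0.5 (√ = 3.937).

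| Analysis | n | z | Naive (bpm) | Correct, ICC 0.1 | Correct, ICC 0.5 |
|---|---|---|---|---|---|
| Final | 300 | 1.9686 | 6.489/√9000 = 0.068 | 0.135 | 0.269 |
| Interim | 150 | 2.9626 | 9.766/√4500 = 0.146 | 0.288 | 0.573 |
| BMI ≥ 30 | 30 | 1.9686 | 6.489/√900 = 0.216 | 0.427 | 0.852 |

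**4. When the verdict changes.** At the final look the naive interval clears −3 if the mean difference exceeds −3 + 0.068 = −2.932. The correct interval at ICC 0.5 needs −3 + 0.269 = −2.731. Only a mean in that strip of about 0.2 bpm changes the 3 bpm verdict. The corresponding strip is −1.932 to −1.731 for the 2 bpm margin, −2.854 to −2.427 at the interim, and −2.784 to −2.148 for 30 BMI ≥ 30 patients at the 3 bpm margin.

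**5. Error with the true bias exactly at the margin.** 1 − Φ(z/√DEFF):
- Final: 1 − Φ(1.9686/1.975) = 0.159 at ICC 0.1, and 1 − Φ(1.9686/3.937) = 0.309 at ICC 0.5, against 0.0245.
- Interim: 0.067 and 0.226, against 0.00153.

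A simulation under other assumed inputs (300 subjects, 60 minutes each, ICC 0.1) gave 21.9% for pooled minutes and 2.2% for subject means at the final boundary.

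**6. Weighting.** Taking a few hours as 180 minutes (assumed) plus 15 PACU minutes gives 195. Against a 10-minute procedure with 15 PACU minutes, the weight ratio is 195/25 = 7.8. Against the 5-minute ITT minimum it is 195/5 = 39.

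**7. Information fraction in minutes.** Assume 15-minute non-anesthesia recordings (30 before the interim, 10 after) and 120 then 140 sedation patients.
- Mean sedation recordings of 40 minutes before the interim and 80 after: (450 + 4800)/(5250 + 150 + 11200) = 0.32.
- Reversed: (450 + 9600)/(10050 + 150 + 5600) = 0.64.
- Constant 60-minute mean: 7650/16200 = 0.47.

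**The case against.** The best reply is that the SAP leans toward the subject. The protocol describes a paired test with all measurements on the same subject. The 150 samples of SAP 7.5.5 are the 150 subjects of 7.1. The concordance analysis (8.2.6) declares repeated measures with a subject identifier, and 9.2.2 averages percent deviations within subject before testing across subjects. Respiratory counts per minute is also simply the unit of respiratory rate, so the quoted sentence may name the variable and not the sample size. In addition, the opening of 9.1 was not available. The amendment table shows that 9.1 holds operative text on the AirRR series that is not visible here, and the unit could be set there.

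This limits the point but does not answer it. On the variable-naming reading, the unit of the overall primary test is still unstated in the visible text. The subject cannot be taken as implied when 9.1.1 uses both bases and MAPE and Bland-Altman work by minute.

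Three stronger readings are tempting and are not supported:
- **The plan treats minutes as independent.** No visible passage says so.
- **The SAP has no subject-level aggregation.** Section 9.1.1 aggregates per subject by period. The gap concerns the overall primary test and which basis decides.
- **The true final half-width is 0.37 bpm against a naive 0.07.** The 0.37 comes from 1.9686 × 3.29647/√300, which treats the Table 6 SD as a subject-level SD, while the 0.07 treats it as a per-minute SD. Both hold together only at ICC = 1.

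It is also fair that SAP 7.5.3 applies no efficacy stopping rule, which reduces the interim consequence. Section 7.5.1 nonetheless lets the interim determine early success.

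**Conclusion.** The point holds as a gap in the visible text: 9.1 names per-minute counts as what is tested, 9.1.1 leaves two bases without precedence, and the boundaries count subjects. If minutes became the unit of inference, the intervals would be too narrow. Under the stated assumptions the understatement is a factor of about 2 to 4, and the final one-sided error at the margin would be about 0.16 to 0.31. Those figures depend on assumed minutes per patient and ICC, and on a true bias exactly at −3. They are not predictions for this trial. The direction needs only positive within-patient correlation.

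The final 3 bpm conclusion is probably safe, because only an observed mean within about 0.3 bpm of the margin would be affected on these inputs. The reported interval, the interim look, the 2 bpm test and small subgroups such as BMI ≥ 30 have less room. This should be fixed, with medium confidence because of the unavailable text.

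**What to change.** In SAP 9.1, beside the sentence on what is tested, state that the subject is the unit of inference, in one of two forms:

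- each subject's mean of AirRR − ManCRR over valid minutes, with a paired (one-sample) t interval; or
- if weighting by monitored time is the intended estimand, pooled minutes with an interval clustered by subject.

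Use the same unit for the interim look, the period and BMI subgroups, and secondary endpoints 4.1 and 4.2. Say in 9.1.1 that the minute-basis results are descriptive. State in Table 6 whether 3.29647 is per minute or per subject, and of what quantity. If the opening of 9.1 already sets the unit, reconcile the rest of 9.1 and 9.1.1 with it.

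The cost is a few sentences and a few lines of code, since per-subject aggregation is already planned by period. The interval will be wider than one from pooled independent minutes, and subject-mean weighting changes the estimand relative to pooled minutes. Power is not a concern: even with 3.29647 as the SD of subject mean differences, 300 subjects give a half-width of about 0.37 bpm and power near 100% at both margins if the true difference is 0.

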9.1.1 Secondary Analyses of Primary Efficacy Endpoint

The primary efficacy analysis will be further divided into three periods of study 1.Induction (3minutes from DIN), 2.Intraoperative period, 3.PACU period to reveal the performance of our device in particular scenarios. The data will be analyzed on a minute basis, and also aggregated per subject basis in each period. The candidates in the non-anesthesia group will be solely analysis for the whole period to represent the normal patient group in a healthcare facility.

| Look | Info Fraction | Approx. Cum. Subjects | Nominal Significance Level (1-sided) | Efficacy Boundaries z-scale |
|---------|---------------|-----------------------------|--|-----------------------------------|
| Interim | 50% | 150 | 0.00153 | 2.9626 |
| Final | 100% | 300 | 0.02450 | 1.9686 |

Fig 6. Information of Interim analysis

the actual measurement of the respiratory event.

9.2.2 Analysis to measure the agreement between AirRR and ManCRR.

Bland Altman analysis, and concordance correlation is adopted to measure the agreement between AirRR and ManCRR. The quantitative results of respiratory rate from these devices under test over time are evaluated by the above mentioned method to analyze the mean and bias from the plot and concordance correlation coefficient.

Fig 9. Bland Altman between AirRR and ManCRR (Example)

Fig 10. Correlation between AirRR and ManCRR (Example)

Fig 11. Correlation between AirRR and ManCRR during induction period (Example)

Evaluating the Non-Inferiority of Airmod to Capnostream™35 on Respiratory Rate Monitoring and User Experience Clinical Evaluation

Fig 12. Correlation between AirRR and ManCRR during Inter-operation period (Example)

Fig 13. Correlation between AirRR and ManCRR during transportation and PACU period (Example)

Also, we apply a sensitivity test for Airmod by comparing the reference method at each time point and calculating the absolute deviations in breaths per minute (bpm). As a measure of accuracy, absolute deviations were calculated as a percent of reference.

Percent absolute deviation were averaged for each subject yielding overall measures of accuracy. To evaluate the accuracy of Airmod, the individual percent absolute deviation was compared for each monitoring time point by subtracting ManCRR from AirRR and then averaged within subject. A paired t test was used to evaluate significance across subjects.

To measure the precision of Airmod for each subject, the standard deviation of percent deviations (in nonabsolute value) was calculated. The precision of Airmod was compared through a paired t test of the subject-specific standard deviations of Airmod's percent deviations from reference.

9.2.3 Analysis to evaluate the response time of the first breath detection followed by administration of jaw thrust during the apnea period. The 3rd secondary objective is to compare the response time of Airmod versus Capnography.

Use paired t-test to compare the response time of Airmod versus Capnography on Capnostream[™]35 after administration of jaw thrust. The target of p<0.05 indicates significance difference.

Evaluating the Non-Inferiority of Airmod to Capnostream™35 on Respiratory Rate Monitoring and User Experience Clinical Evaluation

Fig 14. Breath detection (Capnostream[™]35 & Airmod) followed by administration of jaw thrust during the apnea period

9.2.4 Analysis to compare the influence of subjects to variated breath rates on respiratory rate monitoring in bpm as measured by Airmod, manual-scored and Capnostream[™]35.

In order to determine the performance of Airmod and Medtronic Capnostream[™]35 in the ITT population, we compare them with the gold standard (ManCRR). The difference of ManCRR to AirRR and ManCRR to CapRR are parallel listed and compared to indicates non-inferiority at margin of 3 bpm (M1). The range of respiratory rate are also reported as 95% Confidence Interval of measurement. We proposed to further challenge the largest clinical acceptable range. The difference of ManCRR minus AirRR and ManCRR minus CapRR indicates non-inferiority at margin of 2 bpm (M2) are proposed to be the target of efficacy analysis.

9.2.5 Analysis to evaluate the usability of Airmod.

The demography of users will be shown in pie charts in proportion. (Recorded in [CRF_appendix 9_ Questionnaire POC] Part 1)

The evaluation of usability will be calculated from the Part 2 of [CRF_appendix 9_ Questionnaire POC], the pass rate greater than 90% showed that Airmod is good to manipulate.

10 Safety Analyses

All candidates who were subjected to the device with Airmod and CapnostreamTM35 will be included in the safety analyses (performed in the Safety population) and data will be summarized using descriptive statistics. By reporting the numbers of adverse events (AE)/serious adverse events(SAE) within the trial to indicate the incidence rate of safety issues. We will also present the total number of patients suffering from AE/SAE and its percentage of all populations.

The incidence of adverse events will be tabulated, summarized by intensity and relationship to the investigational product (IP).

• All-Cause Mortality: A table of all anticipated and unanticipated deaths due to any cause, with number and frequency of such events in each arm/group of the clinical study.

Evaluating the Non-Inferiority of Airmod to Capnostream™35 on Respiratory Rate Monitoring and User Experience Clinical Evaluation

- SAEs: A table of all anticipated and unanticipated SAEs, grouped by organ system, with number and frequency of such events in each arm/group of the clinical study. (See AEs definition below).
- Other (Not Including Serious) AEs: A table of anticipated and unanticipated events (not included in the SAEs table) within any subsets of the clinical study, grouped by organ system, with number and frequency of such events in each arm/group of the clinical study.
- ADEs: this category indicates the anticipated device-related adverse events which may be related to the digital stethoscope AS-101.

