6.1.2 DOSING AND ADMINISTRATION

Subjects will be monitored with the devices Airmod and Capnostream™35 simultaneously on Visit 2; both devices should be ready and apply correctly on the subject before sedation.

- Airmod administration procedure

Preparation

1. The device with Airmod should have enough battery life that last for the whole study process. Attach the device with Airmod with the AS-101 using type- C to type-C cable.
2. Place the auscultation sensor on the patient neck (left or right-side plain area of thyroid cartilage), secure with surgical tape.
3. Click on the 'Airmod' on the screen of the device to enter the software interface. When the device with Airmod and AS-101 are properly connected, an indicator light should come up, and then are able to click on the start/stop button to start monitoring.
4. By clicking the start/stop button, immediately breathing sound and spectrogram should be presented via speaker and display screen respectively, and if the signal or reception is unstable, adjust the auscultation sensor or secure with surgical tape to improve.

Monitoring (start time)

5. To start recording the monitoring for the study, on the display screen, select start/ stop button and entering the patient ID.

Monitoring (end time)

6. To end monitoring and terminate the saving process, on the display screen, select the start/stop button. This procedure should be done at the time point where the subject is ready to discharge from post anesthesia care unit (PACU) or the end of non-anesthesia period, which compliance with the criteria PAR or PADSS score ≥ 9 or determined termination by principal investigator.

- Capnostream™35 administration procedure

Preparation

1. Capnostream™35 should have enough battery life that last for the whole study process.
2. To set up for the subject, on the monitoring display screen, select menu -> action -> patient admin -> insert the subject number.
3. Connect the sampling line to the monitor, rotate it clockwise until it can no longer be turned; and also connect the sampling line to the subject nostril, adjust the tightness at the lower band to fit on the subject. When properly connected, the monitor will immediately begin to search breaths, then present EtCO_2 value and waveform on the display screen after 3.4 ~ 5.0 second.

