Activity level	Prior to discharge home, the patient's activity level must be at baseline. Patient must be able to ambulate at preoperative level.
Nausea and vomiting	Prior to discharge, the patient must have minimal to no nausea and vomiting.
Pain	Pain/discomfort must be at a level identified by the patient as tolerable. The location, type and intensity of pain should be consistent with anticipated postoperative discomfort.
Surgical bleeding	The surgical site must be free from excessive or unexpected bleeding/ drainage.

The breathing sounds and the partial pressure of CO₂ will then convert to the breathing counts and CO₂ waveform respectively using self-developed software written from Python and Matlab, the data will be recorded in Microsoft Excel and RR will eventually be calculated manually by trained personnel for each result.

During the study, if the study staff indicates the breathing sounds or the partial pressure of CO₂ is affected, for instance, an obviously external sound, moving the patient, nasal cannula drop, blocked, or other situation identify by the investigator. Such start/stop time of event(s) will be recorded in CRF, accurate to second. Such affected data or missing data will be excluded in the final comparison as such event(s) may be affecting the study result, determined by the investigator during the monitoring period.

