Bland-Altman analysis is used to measure the consistency of continuous data from two distinct measurements. Therefore, the likelihood of AirRR and ManCRR will be quantified and visualized on the assumption of fixed observer and pairs Bland-Altman analysis. It combines the quantitative analysis of LoA (limits of agreement) and the qualitative analysis of scatter plot to show an instinctive evaluation between two methods of their correlation. Each of the n samples is then represented on the graph by assigning the mean of the two measurements as the x-value, and the difference between the two values as the y-value. By this graphical method, we can extend a simple logarithmic transformation approach to data where there is a relationship between difference and magnitude. We discuss the importance of repeatability of RR measurements from each equipment and compare an estimate of this to the LoA. [20] In this case, if the difference of RR measured from two equipment are in the 95% LoA, we will say that RR measured from these two equipment are correlated and acceptable.

$$S(x, y) = \left(\frac{\Delta G_A + \Delta G_E}{2}, \Delta G_A - \Delta G_E \right)$$

3. Use paired t-test to compare the response time of Airmod versus Capnography on Capnostream™35 after administration of jaw thrust. In the target of $p<0.05$ indicates significance. The principal investigator and research members will determine the apnea period and the first effective breath.

The paired t test can be used when the two groups under comparison are dependent on each other. [21] By acquiring the T value from paired t-test, we can obtain the p value indicating the significant difference level via t-distribution table or Microsoft Excel. A p value less than 0.05 would indicate that Airmod is able to resume RR estimation after proper intervention faster than Capnostream™35.

$$t = \frac{\bar{X}_1 - \bar{X}_2}{\sqrt{\frac{(s_1^2 + s_2^2)2\rho s_1 s_2}{n}}}$$

4. Capnography is inherently limited in certain circumstances which may cause ineffectively detecting CO₂, including movement, nasal cannula drop, blocked, or other situations. Airmod is superior to capnography in these limitations since it detects and measure breath sound directly.

4.1 The difference of ManCRR minus AirRR and ManCRR minus CapRR indicates non-inferiority at margin of 3 bpm (M1) and sampling rate 1Hz.

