7.4 Missing Data

(ICH E3; 9.7.1, 11.4.2.2. ICH E9;5.3. EMA Guideline on Missing Data in Confirmatory Clinical Trials)

The missing data in this study is referring to the non-detecting period of each device, which is excluded from the final comparison. The mean non-detecting period will be reported as a baseline variable in the units of minutes. The non-detecting period is the intrinsic NA value from the device record. It could represent the estimation is out of detecting range, or the device is calibrating itself (which is a basic function of the Capnostream[™]35). All of the recorded data will be controlled and monitored by Data and Safety Monitoring Board (DSMB) to ensure data integrity.

In our study, the NA value of intrinsic estimation will show an "NA" or "--" to the user interface of the device, just as the other vital sign monitor. The user interface delivers a clear message for the

malfunction period. It will not affect or increase the risk of respiratory rate measurement.

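### The jaw-thrust response-time comparison drops any event that one device never detects, so a finding of faster covers only the events both devices caught

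*SAP*

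**What the plan says.** The third secondary endpoint compares how soon each device picks up breathing after a jaw thrust given during apnea. SAP 9.2.3 prescribes one analysis: "Use paired t-test to compare the response time of Airmod versus Capnography on" Capnostream 35, and adds "The target of p<0.05 indicates significance difference". Protocol 9.4.3 item 3 reads a significant result in one direction: "A p value less than 0.05 would indicate that Airmod is able to resume RR estimation after proper intervention faster than" Capnostream 35.

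Three general rules govern missing or affected data:

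- SAP 7.4: "The missing data in this study is referring to the non-detecting period of each device, which is excluded from the final comparison". The same section explains that "The non-detecting period is the intrinsic NA value from the device record".
- Protocol 8.1, after listing external sound, moving the patient, and a dropped or blocked nasal cannula as examples: "Such affected data or missing data will be excluded in the final comparison as such event(s) may be affecting the study result".
- SAP 8.3: missing episodes are reported to the DSMB and removed from the final results.

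Non-detection itself is summarised only in aggregate: "The mean non-detecting period will be reported as a baseline variable in the units of minutes". For this endpoint the text gives no maximum observation time, no censoring rule, no value or rank for a device that never detects the breath, and no count of such events by device.

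**The concern.** The endpoint asks which device resumes breath detection sooner after an intervention. On that question, never resuming is the worst possible result. A paired t-test cannot use it, because the event has no second time to subtract, and the general rules treat it as missing data. The comparison is thus restricted to events that both devices detected, and the mean difference does not respond to how often either device fails.

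What is at stake is the directional claim in Protocol 9.4.3. A device that is quick when it works but often fails would look the same as one that is equally quick and never fails. The loss could also work against Airmod: if capnography misses more events, restricting to complete pairs hides an advantage that Airmod really has.

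**Working it through.** **No planned figure to reproduce.** The documents give no number of jaw-thrust events, expected times, SD, non-detection rate or power for this endpoint.

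**What each possible event contributes, reading the rules together**

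| What happens after the jaw thrust | Contribution to the planned t-test |
|---|---|
| Both devices detect the first breath | Difference of two times |
| One device misses the first breath and catches a later one | A longer, finite time; that device is penalised |
| One device never detects, or the event lies in its NA or failure period | None |
| Neither device detects | None |

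The third row is the gap.

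**Illustration 1: how much depends on scoring.** All values are assumed: capnography detects at 8 s in every event; Airmod detects at 4 s in 80% and never in 20%.

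- Complete pairs: 4 − 8 = −4 s (Airmod faster).
- Misses counted at 20 s: 0.8 × 4 + 0.2 × 20 = 7.2 s; 7.2 − 8 = −0.8 s.
- Misses counted at 30 s: 0.8 × 4 + 0.2 × 30 = 9.2 s; 9.2 − 8 = +1.2 s (Airmod slower).
- Misses ranked worst in a signed-rank test: events favouring Airmod hold the lowest 80% of ranks, about 0.8² = 64% of the rank sum. The test still points to Airmod. Its direction changes only when (1 − q)² < 0.5, that is q > 1 − √0.5 = 29%.

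**Illustration 2: break-even miss rate.** Assumed: mean times 8 s (Airmod) and 10 s (capnography), so δ = 2 s; Airmod misses a random share q of events; misses are set to the end of a window W.

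- Complete-pairs difference: −2 s for every q.
- Difference with misses counted: −δ + q(W − 8).
- Break-even: q* = δ/(W − 8) = 2/22 = 9.1% for W = 30 s, and 2/52 = 3.8% for W = 60 s.

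A simulation on these means added SD 3 s, correlation 0.5 and 50 events, with 1,500 trials per row. The table shows W = 30 s and the share of trials significantly favouring Airmod.

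| q | Mean difference, misses at 30 s | Complete-pairs t-test | t-test, misses at 30 s | Sign test, misses ranked worst |
|---|---|---|---|---|
| 0% | −2.0 s | 99.7% | 99.7% | 94% |
| 5% | −2 + 0.05 × 22 = −0.9 s | 99.5% | 29% | 83% |
| 10% | −2 + 0.10 × 22 = +0.2 s | 99.4% | 4% | 64% |
| 20% | −2 + 0.20 × 22 = +2.4 s | 98.7% | 0% | 21% |
| 30% | −2 + 0.30 × 22 = +4.6 s | 96.9% | 0% | 4% |

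The complete-pairs column barely moves. The small fall reflects fewer pairs (50 down to 35), not a change in the estimate.

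**Opposite direction.** Assumed: both devices average 10 s, W = 30 s, and capnography misses 10% or 20%. Complete pairs show a difference of about 0 and favour Airmod in 2–3% of trials. With misses counted, the difference is −0.10 × 20 = −2.0 s or −0.20 × 20 = −4.0 s.

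**The case against.** SAP 9.2.3 and Protocol 9.4.3 item 3 state no exclusion for this endpoint, and the failure-period paragraphs in Protocol 9.4.2 and 9.4.3 are worded for the paired non-inferiority test. SAP 7.4 also fits awkwardly here: the endpoint starts in apnea, when neither device should be detecting breaths, so a literal reading would delete the period under study. That ambiguity stands. It does not close the gap, because a paired t-test loses any event without two times whether or not an exclusion rule is invoked.

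Some handling already exists. SAP Table 8 logs EtCO2 failure (ETF) and Airmod failure (AMF) with start and end times, and SAP 7.4 reports a mean non-detecting period. Neither reaches the response-time analysis or gives counts per jaw-thrust event. Figure 14, which depicts the measurement, and part of the text around SAP 9.1 were not available to this review.

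A reader might also infer three stronger points that the documents do not support:

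- **That every missed first breath is treated as missing.** It is not. Catching a later breath gives a longer finite time, which stays in the test.
- **That the bias runs in Airmod's favour.** Protocol 6.1.2 says "Place the auscultation sensor on the patient neck", close to where a jaw thrust is applied, and Protocol 8.1 excludes external sound and patient movement. But the same sentence in 8.1 lists a dropped or blocked cannula, which are capnography failures. No failure rate is given for either device, so the direction is unknown.
- **That the result would reverse.** The reversals above come from averaging in misses at an assumed 30 s or 60 s. With worst ranks, the 20% example still favours Airmod.

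**Conclusion.** The gap is real and should be closed before analysis. As written, the endpoint estimates the mean time difference among events that both devices detected, while the protocol interprets it as one device resuming sooner. Events that a device never detects, or that fall in its NA or failure period, are lost from the comparison and are not counted anywhere for this endpoint.

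The size cannot be fixed from the documents. Under the assumed inputs in Illustration 2, the mean difference changes sign at miss rates of 9.1% (30 s window) or 3.8% (60 s window). A worst-rank test is far less sensitive to the window. These figures show that the planned test cannot reveal the problem; they do not predict this trial's result. They assume misses occurring at random and independent events.

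This is one secondary endpoint, and the primary non-inferiority conclusion is not affected.

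**What to change.** Add the following to SAP 9.2.3 and align Protocol 9.4.3 item 3:

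1. **Event set.** Include every jaw thrust given during apnea, identified from codes APN and JWT in SAP Table 8.
2. **Window.** Prespecify one fixed observation window after the jaw thrust, with its length justified by the sponsor. A cut-off at the next logged event would be arbitrary, because Table 8 also logs things such as friction sound and bed movement that may follow within seconds.
3. **Non-detection.** Treat non-detection by the end of the window as worst rank or as censored, in a paired analysis that allows for several events per subject. Count events missed by both devices as ties.
4. **Exclusions.** Do not drop an event from this endpoint solely because a device returned NA. Show events with a logged ETF or AMF failure separately in a sensitivity analysis. Lifting every exclusion outright would go too far, since it would score self-calibration or a dislodged cannula as a detection failure.
5. **Reporting.** Tabulate events detected by both devices, Airmod only, capnography only and neither.
6. **Supportive analysis.** Keep the complete-pairs t-test, labelled as describing events that both devices detected.

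The cost is SAP wording and modest programming; the event codes are already collected. A rank-based or censored summary becomes the main result in place of the mean difference. The result may look less favourable for whichever device misses more events.
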